Along with standard anesthesia regimen, the anesthesiologist during the case will take arterial blood gases (ABGs). An arterial line will be placed since the subject is in the prone position to keep close surveillance on perfusion pressure. An arterial line is not placed in all robotic prostatectomy patients and is used in those who require more careful and continuous blood pressure monitoring. For the study, all patients who consent to participate will have an arterial line. An arterial line is a very small catheter similar to an IV catheter used in all surgical procedures but placed in an artery instead of a vein. It will be placed by anesthesia (not nursing). The risks are similar to an IV, such as bruising/bleeding/hematoma at the site of insertion. The arterial line will be removed at the end of the operation per routine practice unless required for postoperative blood pressure monitoring in PACU. The arterial line kit cost will be accounted for in the study budget. If in the opinion of the anesthesiologist an arterial line is not feasible, a 20 gauge needle catheter will be placed in the radial artery post-induction for samples to be taken intermittently during the surgery.

Samples will be taken at baseline beginning at insertion of the catheter, 60 minutes after insufflations, and at the end of the procedure. ABGs will be analyzed for PaCO₂, HCO₃, PaO₂ and pH. Study staff will document all values that are produced from ABGs. Data points (such as PIP, PEEP, end-tidal CO₂ etc.) from the anesthesia machine will be automatically uploaded into CareConnect. Subjects will undergo their surgical procedure regardless of participation in this study. The AirSeal® System is commercially available and in clinical use. There are no additional direct costs to participants in this study. The principal risk specifically associated with participation in this study is potential loss of confidentiality. Participants in this study are not exposed to any additional or different risks associated with the surgery. If randomized to the AirSeal® System, potential benefits to participation in the study include decreased need for port removal for removal of foreign bodies and native tissues, placement of prosthetics, and scope de-fogging and smoke evacuation.

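### The risk summary in section 2.4 omits the arterial cannulation that the study requires of every participant, and no listed variable or described adverse event procedure specifically captures its complications

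*Combined protocol and SAP*

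**What the plan says.** All the risk statements are in section 2.4 (Study Design).

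On usual care: "An arterial line is not placed in all robotic prostatectomy patients and is used in those who require more careful and continuous blood pressure monitoring".

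On the trial: "For the study, all patients who consent to participate will have an arterial line". The kit is charged to the study budget. If the anesthesiologist judges a line not feasible, "a 20 gauge needle catheter will be placed in the radial artery post-induction for samples to be taken intermittently during the surgery".

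On the hazards of the line: "The risks are similar to an IV, such as bruising/bleeding/hematoma at the site of insertion".

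On the risk of taking part, later in the same section: "The principal risk specifically associated with participation in this study is potential loss of confidentiality", followed by "Participants in this study are not exposed to any additional or different risks associated with the surgery".

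On data, Table 2 in section 2.3 lists the study variables. Those closest to complications are blood loss, loss of pneumoperitoneum, AirSeal malfunctions, nausea and vomiting, and wound infection. The text below the table undertakes to collect surgical outcomes up to PACU discharge and rules out longer follow-up.

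**The concern.** The section describes an invasive procedure that goes beyond usual care for some participants, names its harms, and then sums up the risk of participation without it. The blood gas samples drawn through the catheter supply PaCO₂, which section 1.2 calls the primary observation. The cannulation is therefore a core study procedure.

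Two things are at stake. The first is the accuracy of the risk description that investigators and the ethics board rely on. The second is safety reporting. If no variable is set aside for arterial-site events, the trial may end without a count of harms from the one invasive procedure it adds, and could not then give even an upper limit for their frequency.

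**Working it through.** The protocol gives no figure on this point, so there is none to reproduce. The check is mainly textual.

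**Step 1: is cannulation part of participation?** Section 2.4 says that not all such patients get a line and that all participants will. The fallback also enters an artery, so every participant is cannulated whichever route is used. The section gives a clinical reason as well (positioning and surveillance of perfusion pressure). That reason does not explain why all participants need a line when, by the protocol's own account, not all such patients have one. The two reasons should be reconciled.

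**Step 2: does the risk summary include it?** No. It names confidentiality as the principal risk and makes a no-additional-risk statement about the surgery. The bruising, bleeding and hematoma described for the line do not reappear.

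**Step 3: is there a route for recording its complications?**

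| Place | What it covers | Arterial-site events? |
|---|---|---|
| Table 2, intraoperative, PACU and Day 1 lists | Named variables | No item |
| Section 2.3, text below Table 2 | Surgical outcomes to PACU discharge | Possible on a broad reading; not named |
| Section 2.3, confidentiality text | Release of the subject key for device-related adverse events reportable to the FDA | No |
| Section 2.4, malfunction text | Safety follow-up after an AirSeal malfunction, with study data recording stopped | No |
| Section 2.4, removal criteria | A serious or intolerable adverse event as a reason for removal | Only if that severe, and no collection method is given |
| Appendices C and D | Data collection forms and tool | Not shown; cannot be judged |

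**Step 4: scale.** Section 2.2 plans N = 100. Let s be the unknown share who would have had a line anyway, and p the complication rate. The number cannulated only because of the study is 100 × (1 − s), which runs from 0 (s = 1) to 100 (s = 0). The documents give neither s nor p.

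For orientation only, with p **assumed**, the expected count among all participants is 100 × p, and the chance of at least one event is 1 − (1 − p)^100:

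| Assumed p | Expected events | Chance of at least one |
|---|---|---|
| 0.5% | 0.5 | 39% |
| 1% | 1 | 63% |
| 2% | 2 | 87% |
| 5% | 5 | 99% |
| 10% | 10 | about 100% |

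These counts cover all lines. The excess due to the study is smaller by the factor (1 − s).

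If events were recorded and none occurred in 100, the exact upper 95% limit would be 1 − 0.05^(1/100) = 3.0% (one-sided) or 1 − 0.025^(1/100) = 3.6% (two-sided). Without recorded counts, no such limit can be stated.

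**The case against.** The strongest defense is that the wording is narrower than it looks. Calling a risk the principal one ranks it and does not exclude others. The no-additional-risk sentence is limited to risks associated with the surgery. Section 2.4 also says standard operative procedures apply regardless of participation, so the sentence can fairly be read as being about the operation, whereas the line is placed by anesthesia. The line's risks are set out a few sentences before, so a reader of the whole section is not left unaware of them.

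That defense stands against a stronger inference a reader might draw: that the protocol denies any risk beyond confidentiality, or conceals the risk of the line. The text supports neither. The defense does not rescue the summary, which still ranks confidentiality above an invasive procedure required of everyone, without argument, and leaves that procedure out.

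A reader might also infer that arterial complications will not be collected at all. That goes too far. The data collection forms are attached but not shown, and the promise of surgical outcomes to PACU discharge could be stretched to include such events. What can be said is that no listed variable or described procedure names them. That promise also stops at PACU discharge, although section 2.4 lets the line stay in during PACU when blood pressure monitoring requires it.

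Nothing can be inferred about what patients were told, because the consent form is not available.

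Finally, it can be said that no result changes. That is correct for the comparison between arms, since both get the line. It is no answer on safety reporting.

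**Conclusion.** The point holds as an internal inconsistency in the risk description, together with a gap in the listed safety variables. By the protocol's own statements, every participant is cannulated, not every such patient would be, and the procedure has named harms. The closing risk summary leaves it out, and neither Table 2 nor the adverse event wording specifically provides for recording those harms.

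The size is limited. All 100 planned participants are exposed, but the number exposed only because of the study is unknown, and the complication rates above are assumptions. Better wording and one more variable would improve how risk is described and reported; they would not change anyone's exposure. The efficacy analysis is untouched.

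The conclusion rests on the text available. If the data collection forms already carry an arterial-site item, the recording gap closes and only the wording remains to be corrected. The correction should still be made, because the issue concerns participant safety and costs little to put right.

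**What to change.** 1. Reconcile the statements in section 2.4. List arterial cannulation, with the risks already described there, as a study-related risk for participants who would not otherwise have a line. Word the no-additional-risk sentence so that it plainly refers to the operation itself. Bring the positioning reason and the study reason for the line into agreement.
2. Add one item to the PACU list and the Day 1 list in Table 2: arterial-site complication (bruising, bleeding, hematoma). For patients discharged before 0700, ask about it during the morning call that section 2.3 already schedules for urine output.
3. Report the counts by arm.

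The cost is a wording change, one data item and one extra question on that call. The Day 1 answer from patients at home would be self-reported, not observed, and should be labeled so. Sample size and the efficacy analyses stay as they are.

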- General or specific changes in the subject's condition that render further treatment unreasonable or unsafe within the standards of clinical practice in the judgment of the Principal Investigator or treating physician

2.5 – Statistical Analysis

We will first compare the demographic and pre-operative clinical characteristics of the conventional and valve-less trocar groups to evaluate randomization fidelity. If any characteristics are found to be statistically significant between the groups, this will be accounted for in the analyses of the primary and secondary outcomes. We will describe all categorical variables as percentages and continuous variables with means and standard deviations.

Aim #1) Describe the perioperative CO₂ absorption rates between the conventional and valve-less trocar groups via the end-tidal CO₂ and PaCO₂ , at baseline, 60 minutes intraoperatively, and immediately following surgery. We will also examine the valve and valve-less trocar groups on their ability to maintain acceptable ABG levels by comparing the number of interventions required by the anesthesiologist during the procedure between groups.

We will describe the change in CO₂ and PaCO₂ levels at 3 intervals: baseline to 60 minutes, 60 minutes to end of surgery, and baseline to end of surgery to examine the trends in both groups. We will compare the conventional and valve-less trocar groups on the number of interventions required by the anesthesiologist to maintain acceptable pressure using Poisson regression. If a significant number of patients required no intervention we will use a zero-inflated model. Statistical significance will be set at p<.05. We will also compare CO₂ absorption rates between high pressure (>8mmHg) and low impact (≤8mmHg) procedures.

Aim #2) Compare the maximum pneumoperitoneal pressure (mmHg), smoke evacuation quality (categorical), and overall operative times (minutes) between the conventional and valve-less trocar groups.

We will compare the conventional and valve-less trocar groups on maximum pneumoperitoneal pressure and overall operative time using t-tests or Wilcoxon rank sum tests. We will compare the groups on evacuation quality using a chi-square test. Statistical significance will be set at p<.05.

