Aim #3) Compare pain scores through discharge from the preoperative and post-anesthesia care units (PACU) by monitoring self-reported pain ratings using an 11-point numerical rating scale (NRS-11) and pain medication usage via morphine equivalent dose (MED) units.

To evaluate our this outcome we will use a linear mixed model with pain score as the dependent variable and treatment group and time as independent variables. Mixed models are often preferred over a two-way ANOVA because they allow for incomplete data from participants and do not require a strictly normal distribution in the dependent variable. We will also examine the difference in MED units between groups using a t-test. Statistical significance will be set at p<.05.

[figure not shown]

3.0 - REFERENCES

- 2) McCarus SD, et al. Gynecological laparoscopy: improving laparoscopic herniation outcomes without trocar site fascial closure: a multicenter trial. Presented at: American College of Surgeons 90th Annual Clinical Congress; October 10-14, 2004: New Orleans, LA.
- 3) Ethicon Endo-Surgery. "Endopath Xcel Bladeless." *Xcel Bladeless*. Endopath, 2010. Web. 18 Sept. 2012. <<http://www.ethiconendosurgery.com/xcelbladeless>>.
- 5) A new Valve-Less Trocar for Urology Laparoscopy: Initial Evaluation. *Journal of Endourology* 2009;23: 1535-39.
- 6) Herati et al. Use of the valveless trocar system reduces carbon dioxide absorption during laparoscopy when compared with standard trocars. *Urology* 2011; 5: 1126-1130.

4.0 - APPENDICES

A. Numerical Rating Scale (NRS-11)

Pain monitoring schedule by RN in PACU using NRS-11.

Timepoint	Definition
Baseline	Prior to surgery
Post-operatively	After surgery & after anesthesia completion

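### Section 2.5 adjusts for a baseline characteristic only after a significant imbalance, so prognostic covariates are mostly left out and no adjusted model is fixed in advance

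*Combined protocol and SAP*

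**What the plan says.** Section 2.5 begins with a plan to "compare the demographic and pre-operative clinical characteristics of the conventional and valve-less trocar groups to evaluate randomization fidelity". It continues: "If any characteristics are found to be statistically significant between the groups, this will be accounted for in the analyses", and applies this to primary and secondary outcomes alike. It does not list the characteristics, give a significance level for the screen (p<.05 is set under each aim), or say how a flagged variable would be handled. Section 2.4 describes computer-based randomisation to two groups and names no stratification factor, so the plan has no other route to a covariate.

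The analyses named in Section 2.5 are:

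- **Aim 1, CO₂ levels:** changes are described over three intervals, "baseline to 60 minutes, 60 minutes to end of surgery, and baseline to end of surgery to examine the trends in both groups". No test between arms is named.
- **Aim 1, ventilation adjustments:** the arms are compared on "the number of interventions required by the anesthesiologist to maintain acceptable pressure using Poisson regression", with a zero-inflated model as fallback.
- **Aim 2:** "maximum pneumoperitoneal pressure and overall operative time using t-tests or Wilcoxon rank sum tests". For smoke: "We will compare the groups on evacuation quality using a chi-square test".
- **Aim 3:** for pain, a "linear mixed model with pain score as the dependent variable and treatment group and time as independent variables". For medication: "We will also examine the difference in MED units between groups using a t-test".

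None of these names a baseline covariate.

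**The concern.** A baseline test in a correctly randomised trial asks whether chance produced an imbalance. It does not ask whether the variable predicts the outcome, and that is what decides whether adjustment helps. A significance trigger therefore tends to omit useful covariates and sometimes brings in useless ones.

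The rule also cannot be carried out as written for four of the tested outcomes, because a t-test, a rank-sum test and a chi-square test have no place for a covariate. If a variable were flagged, someone would have to choose the new model with the data in view. At stake are precision and freedom from analyst choice in the intervention count and in Aims 2 and 3.

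**Working it through.** **Inputs.** Section 2.2 gives 100 patients in total. The documents state no power, effect size or standard deviation, so there is no figure of the plan's own to reproduce. Assumed here: 50 per arm, a two-sided screen at 0.05, and 8 independent characteristics. Table 2(a) suggests about 8: age from date of birth, BMI, weight, medical history, surgical history, creatinine, hemoglobin and preoperative pain. BMI and weight are correlated, which lowers the figures in step 2 somewhat.

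**1. How often a given prognostic baseline is left out.** With a screen at level a, this is 1 − a: 95% at 0.05, 99% at 0.01 and 90% at 0.10.

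**2. How often the screen flags something.** The chance is 1 − (1 − a)^K.

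- a = 0.05: 1 − 0.95⁴ = 0.185; 1 − 0.95⁸ = 0.337; 1 − 0.95¹² = 0.460.
- K = 8: 1 − 0.99⁸ = 0.077 and 1 − 0.90⁸ = 0.570.

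**3. Precision, by hand.** Take a normal outcome with SD 1 and correlation ρ with one baseline. Set the effect for nominal 80% power with that covariate in the model: δ = 2.80 × √[(1 − ρ²) × 2/50]. The expected z is 2.80 adjusted and 2.80 × √(1 − ρ²) unadjusted, and power is about Φ(z − 1.96).

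| ρ | z unadjusted | Power unadjusted | Power adjusted | Points forgone |
|---|---|---|---|---|
| 0.1 | 2.786 | 79.6% | 80.0% | 0.4 |
| 0.2 | 2.743 | 78.3% | 80.0% | 1.6 |
| 0.3 | 2.671 | 76.1% | 80.0% | 3.8 |
| 0.5 | 2.425 | 67.9% | 80.0% | 12.1 |

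**4. Precision under the rule, by simulation.** Same δ, with 1 prognostic and 7 irrelevant independent baselines; flagged ones are added to a linear model.

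| ρ | Unadjusted | Rule | Covariate named in advance |
|---|---|---|---|
| 0.2 | 77.5% | 76.6% | 79.2% |
| 0.3 | 75.0% | 74.4% | 78.4% |
| 0.5 | 67.4% | 67.6% | 79.3% |

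The rule loses 2.6, 4.0 and 11.7 points against the named covariate. A separate run of 20,000 trials per setting gave 78.5 − 76.7 = 1.8, 78.9 − 74.7 = 4.2 and 78.9 − 67.0 = 11.9 points. It also gave 78.9 − 78.2 = 0.7 at ρ = 0.1 and 78.3 − 77.8 = 0.5 at ρ = 0. Against the unadjusted test, the rule differs by 0.9, 0.6 and −0.2 points in the table, which is close to simulation noise.

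**5. Type I error in the linear model.** Followed mechanically, the rule gave 5.1, 5.2, 4.8, 4.8 and 4.4% at ρ = 0, 0.1, 0.2, 0.3 and 0.5. Taking the smallest p-value among the unadjusted, all-flagged, each-flagged and Wilcoxon analyses gave 6.0 to 6.7%.

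**6. Can the named analyses carry out the rule?**

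| Outcome | Named analysis | Holds a covariate? |
|---|---|---|
| Intervention count | Poisson or zero-inflated | Yes, none named |
| Maximum pressure, operative time | t-test or Wilcoxon | No |
| Smoke quality | Chi-square | No |
| Pain score | Linear mixed model | Yes, none named |
| MED | t-test | No |

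**The case against.** The strongest reply is that an unadjusted comparison in a randomised trial is valid, so the power losses are a gain not taken rather than damage done by the trigger. That stands: step 4 shows that the trigger itself costs about a point or less.

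It also stands that the documents give no correlation, effect size or power target, and nothing in them shows that BMI or age predicts these outcomes. The data collection forms are listed as appendices but are not in the text reviewed. They may code medical and surgical history, so the most one can say is that Section 2.5 does not list what is screened.

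A further reply is that the plan commits to accounting for flagged variables, which leaves no licence to pick the best result. This holds only in part: for four outcomes there is no named model to follow, so some choice is unavoidable once a variable is flagged.

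Three stronger readings are tempting and are not supported:

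- **The trigger inflates false positives in the Poisson analysis.** With ordinary standard errors, a mean count of 4 and a log rate ratio of 0.3 per SD of an omitted covariate (assumed values), type I error is 9.9% with no adjustment and 9.0% under the rule. It is about 5% with robust standard errors. The cause is the Poisson variance assumption.
- **The trigger dilutes the pain effect.** Keeping baseline pain as an outcome row is a separate question. Dilution would also require that no group-by-time term be fitted, and Section 2.5 does not settle that.
- **The comparison of PaCO₂, which Section 1.2 calls the primary observation, is compromised.** Section 2.5 only describes PaCO₂ and end-tidal CO₂ changes between arms, so there is no test to distort.

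**Conclusion.** The point holds and should be changed. The trigger carries no information about prognostic value, and for maximum pressure, operative time, smoke quality and MED it cannot be applied without choosing a model after seeing the data. That part rests on the text alone and is firm.

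The size is conditional. Precision forgone is about 2, 4 and 12 power points at correlations of 0.2, 0.3 and 0.5, assuming a normal outcome, 50 per arm and a true effect giving nominal 80% adjusted power. It is under 1 point at 0.1 or less. No type I inflation is shown in a linear model if the rule is followed mechanically; the 6 to 7% figure applies only if the best of several analyses is reported.

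**What to change.** - Delete the significance trigger and keep the baseline table descriptive.
- Name now a short list of covariates already collected and expected to be prognostic, for example BMI and age, and use them whatever the imbalance.
- Put them in a linear model for maximum pressure, operative time and MED, in the Poisson model, and in the pain mixed model. For postoperative pain, add the preoperative NRS score as a covariate.
- State that smoke quality keeps its unadjusted chi-square test.
- Use robust standard errors in the Poisson model as a separate safeguard against overdispersion, not as a remedy for the trigger.

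The cost is analysis wording only. BMI, date of birth and preoperative NRS are in Table 2(a), but age must be derived before the de-identification that Section 2.3 places ahead of analysis. The downside is slightly more modelling than two-sample tests, and little gain if the chosen covariates are weakly prognostic.
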